#### 9.6.5 Vital Signs

For vital signs (temperature, pulse, and blood pressure) and weight, summary statistics (n, mean, standard deviation, median, minimum, the 25th (Q1) and 75th (Q3) percentiles, and maximum) of observed and change from baseline values will be presented. For vital signs (excluding weight), shift from baseline to each post-baseline visit, to worst (low/normal/high/both low and high) and to end of phase/period in below, within and above the normal ranges will be displayed in cross—tabulations for the Placebo-controlled Phase and for the Apremilast-exposure Period for parameters included in below Table 4. For weight, change from baseline (and percent change from baseline) to end of phase/period will be presented, as well as by baseline and baseline weight categories.

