Treatment-emergent AEs were predominantly mild or moderate in severity. The most frequently reported TEAEs (ie, diarrhea, nausea, upper respiratory tract infection, and headache) were primarily mild in severity. Severe diarrhea was reported by 1 (0.1%) subject in the placebo group, 4 (0.4%) in the APR 20 BID group, and 3 (0.3%) in the APR 30 BID group. Severe nausea was reported by 0 subjects in the placebo group, 2 (0.2%) in the APR 20 BID group, and 3 (0.3%) in the APR 30 BID group. Severe headache was reported by 1 (0.1%) subject in the placebo group, 2 (0.2%) in the APR 20 BID group, and 1 (0.1%) in the APR 30 BID group. No events of severe upper respiratory tract infection were reported in any treatment group. Treatment with apremilast was associated with an increase in adverse reactions of depression. During the 0-to-16-week placebo-controlled period of Palace 1, 2, and 3, 1.0% (10/998) of patients treated with apremilast reported depression or depressed mood and 0.8% (4/495) treated with placebo.

^a Preferred terms are coded using MedDRA Version 14 and are presented in descending order of subject incidence in the APR Total group. A subject with multiple occurrences of an AE is counted only once in the AE category.

^b The first 16 weeks of exposure are included regardless of when apremilast exposure started.

Body weight was measured routinely in Studies CC-10004-PSA-002, CC-10004-PSA-003, CC-10004-PSA-004, and CC-10004-PSA-005. At the end of the placebo-controlled period, median (mean) weight change from baseline was 0.00 (0.13) kg in the placebo group, -0.50 (-1.05) kg in the APR 20 BID group, and -0.60 (-0.97) kg in the APR 30 BID group. Weight loss > 5% was observed in 2.1% of subjects in the placebo group, 4.7% in the APR 20 BID group, and 4.9% in the APR 30 BID group.

Serious TEAEs were reported for 22 (3.3%) subjects who received placebo and 44 (2.3%) who received apremilast during the first 16 weeks of exposure (Table 9). The incidence of serious adverse events (SAEs) was comparable across treatment groups, ie, 3.3% of subjects in the placebo group, 2.4% in APR 20 BID group, and 2.2% in the APR 30 BID group.

Table 9: Treatment-Emergent Serious Adverse Events Reported in > 1 Subject in Any Treatment Group, First 16 Weeks of Exposure (Studies CC-10004-PSA-002, CC-10004-PSA-003, CC-10004-PSA-004, and CC-10004-PSA-005; Subjects as Treated)

	Weeks 0 to 16	First 16 Weeks of Apremilast Treatmen		

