6.5.2. Vital Signs, Height and Weight

Vital signs, including temperature, pulse, and seated blood pressure, will be taken during the visits indicated in Table 13, Table of Events. Height will be measured and recorded at Screening; weight will also be measured and recorded at every visit.

In the event of unexplained and clinically significant weight loss, subjects should be evaluated and discontinuation of study treatment should be considered by the Investigator.

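### SAP 9.6.5 plans no count of subjects by measured weight loss, although the protocol describes this apremilast risk as the percentage losing more than 5%

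*SAP*

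**What the plan says.** - **The risk and how it is expressed.** Protocol 1.2.1.2, on the pooled phase 3 data, reports "Weight loss > 5% was observed in 2.1% of subjects in the placebo group", against 4.7% on 20 mg BID and 4.9% on 30 mg BID. The same paragraph gives the average picture: "median (mean) weight change from baseline was 0.00 (0.13) kg in the placebo group", and -0.60 (-0.97) kg on 30 mg BID.
- **Why weight is monitored.** Protocol 6.5.2 states that "weight will also be measured and recorded at every visit" and continues: "In the event of unexplained and clinically significant weight loss, subjects should be evaluated and discontinuation of study treatment should be considered by the Investigator". It attaches no percentage to that instruction.
- **The endpoint.** Protocol Table 12 and SAP 2.1 list a safety endpoint on how often clinically significant changes occur in examination findings, vital signs or laboratory values. Protocol 9.7 counts weight among the vital signs.
- **The planned analysis.** SAP 9.6.5 gives weight the usual statistics (n, mean, SD, median, minimum, quartiles, maximum) for observed and change values, and SAP 9.6.1 has continuous safety variables summarised at each time point. SAP 9.6.5 adds: "For weight, change from baseline (and percent change from baseline) to end of phase/period will be presented", also by baseline weight category. The shift tables are for other variables: "For vital signs (excluding weight), shift from baseline to each post-baseline visit, to worst".
- **Where a weight criterion could have stood.** SAP Table 4 (normal ranges), SAP Table 6 (marked abnormalities) and the visible text of SAP 9.6.3 (adverse events of special interest) contain none.

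**The concern.** The protocol's evidence on this risk is a proportion above a threshold, and the endpoint is a frequency. The SAP summarises the distribution of weight and never converts it into a number of subjects. Laboratory analytes get incidence and exposure-adjusted rates of marked abnormalities, and pulse and blood pressure get shifts to worst value. Weight, which has its own monitoring instruction, gets neither.

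At a rate near 5%, the affected subjects sit in the far tail. The report could show a median change well under 1 kg and still leave the reader unable to say whether 2% or 10% of subjects lost more than 5%. The trial could then not be set beside the figure its own protocol quotes. A subject with a marked loss at Week 12 that is partly regained by Week 24 would also be in no count by measured weight.

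**Working it through.** **1. The stated figure.** The rates of 2.1%, 4.7% and 4.9% come without numerators or denominators, so they cannot be reproduced. They are used below as inputs.

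**2. Is there any count by measured weight?**

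| Planned output | Gives a number of subjects above a weight-loss threshold? |
|---|---|
| Summary statistics by time point (SAP 9.6.1, 9.6.5) | No: location, spread, quartiles, extremes |
| Change and percent change to end of phase (SAP 9.6.5) | No: the right variable, but no cut-off |
| Shift tables (SAP 9.6.5, Table 4) | No: weight excluded |
| Marked abnormalities (SAP 9.6.4, Table 6) | No: laboratory analytes only |
| Adverse events of special interest (SAP 9.6.3, visible text) | No: diarrhea |
| Treatment-emergent adverse event tables (SAP 9.6.2) | Only losses an investigator reports; no measured threshold |

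**3. Can the planned statistics stand in for the count?** With 4.9% of subjects affected, about 95% are not, so the first quartile does not reach them. The minimum shows the single largest loss, not how many exceed 5%.

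To see what the mean alone conveys, take the historical mean of -0.97 kg. Assume (not from the documents) normally distributed percent change, baseline weight w of 75 to 95 kg and an SD of 2 to 4 percentage points. Then the share losing more than 5% = Φ[(-5 + 100 × 0.97/w)/SD].
- w = 95, SD = 2: (-5 + 1.02)/2 = -1.99, giving 2.3%.
- w = 75, SD = 4: (-5 + 1.29)/4 = -0.93, giving 17.7%.

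A reported SD would narrow this range, but only under normality. The historical mean on 30 mg BID lies 0.97 - 0.60 = 0.37 kg below the median, which suggests a longer tail on the loss side.

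**4. Expected counts.** Arm sizes are redacted; 285 at 2:1 gives 285 × 2/3 = 190 and 285 × 1/3 = 95.
- Apremilast: 190 × 0.049 = 9.3. Placebo: 95 × 0.021 = 2.0.
- If 15% have no value (the SAP 3.2 dropout rate, applied here by assumption): 161.5 × 0.049 = 7.9 and 80.75 × 0.021 = 1.7.

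**5. What the count could show.** With 9/190 (4.7%) and 2/95 (2.1%):
- Exact 95% intervals: 2.2% to 8.8% and 0.3% to 7.4%.
- Difference +2.6 points, Newcombe 95% interval -3.1 to +6.9.
- Power for 4.9% against 2.1%, two-sided 0.05: pooled proportion (9.31 + 1.995)/285 = 0.0397; standard error under the null √[0.0397 × 0.9603 × (1/190 + 1/95)] = 0.0245; under the alternative √[0.049 × 0.951/190 + 0.021 × 0.979/95] = 0.0215. Power = Φ[(0.028 - 1.96 × 0.0245)/0.0215] = Φ(-0.93), about 18%.

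The count is descriptive, which is how SAP 9.6.1 treats safety throughout.

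**The case against.** The case against has real force, and it rules out several stronger readings.

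- **A reader might infer that affected subjects are never counted.** They can be. Protocol 10.1 defines adverse events broadly, and a reported weight loss enters the SAP 9.6.2 tables, including those for drug interruption and withdrawal. That route suits the unexplained, clinically significant cases that protocol 6.5.2 has in mind. But neither document says what measured loss makes an adverse event, so those counts depend on investigator judgment and cannot be compared with a measured 5% rate.
- **A reader might infer that weight is reported mainly as an average to end of phase.** The plan is fuller: quartiles and extremes at each time point are included. A loss at Week 12 is in the Week 12 distribution.
- **A reader might treat leaving weight out of the worst-value shift as a defect.** It is not. That table classifies values as low, normal or high against the ranges in SAP Table 4, and weight has no such range there. Its absence from Table 6, a laboratory table, shows nothing either.
- **A reader might want a second cut, such as 10%.** No such figure appears in the documents.
- **The endpoint argument is open to dispute.** Protocol 6.5.2 names temperature, pulse and blood pressure as vital signs and treats weight alongside them. Protocol 9.7 does group weight with vital signs, but promises it only a descriptive summary by visit, which the SAP delivers.
- **The 5% figure is background data.** The protocol does not make it a monitoring rule or an endpoint criterion, and the power is low.

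What remains is that none of the planned weight statistics yields the proportion by which the protocol itself describes the risk.

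**Conclusion.** The point holds in a limited form. SAP 9.6.5 omits a count of subjects by measured weight loss, and the statistics it does plan cannot supply one. The size is small: about 9 apremilast and 2 placebo subjects at the historical rates.

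This rests on three assumptions: arms of 190 and 95; rates carried over from earlier trials that required at least three swollen and three tender joints; and the historical 5% figure being an end-of-period value. The protocol paragraph opens its weight results at the end of the placebo-controlled period, which makes the third likely but does not settle it. On that reading, the percent change the SAP already derives at end of phase is the matching variable and only the cut-off is missing. A count at any visit would be an addition, at least as large as the end-of-phase count, and not a like-for-like comparison.

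No hypothesis test, sample size or efficacy conclusion is affected. The change is still worth making because it ties the safety report to the protocol's own figure at almost no cost.

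**What to change.** In SAP 9.6.5 add the number and percentage of subjects with weight loss of more than 5% from baseline:

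- at end of phase, for comparison with protocol 1.2.1.2; and
- at any post-baseline visit.

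Present both by arm for the Placebo-controlled Phase and for the Apremilast-exposure Period, using the baselines in SAP 5.3. Use as denominator the subjects with a baseline and at least one post-baseline weight, the convention SAP 9.6.4 already applies to criteria that need a baseline.

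For the any-visit count, add the exposure-adjusted incidence rate defined in SAP 9.6.1. Under SAP 5.5, placebo subjects who escape early leave the Placebo-controlled Phase at Week 16, while apremilast subjects can contribute to Week 24. Crude percentages at any visit would therefore rest on unequal observation time.

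Label the table descriptive. It reports a proportion and sets no clinical rule. The cost is one additional table; the weights are already scheduled, so no new assessment is needed.

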**Table 4. Normal Ranges for Shift Table** 

Vital Sign Parameter	Normal Ranges
Pulse	60 – 100 beats/minutes
Systolic blood pressure	90 – 140 mmHg
Diastolic blood pressure	60 – 90 mmHg

#### 9.6.6 Physical Measurements

Physical examination findings will be captured as medical history at screening. Abnormal physical examination findings post Screening will be reported as adverse events and will be reported in the summaries.

#### 9.6.7 Electrocardiogram

Not applicable.

#### 9.6.8 Antibody Formation

Not applicable.

#### 9.6.9 Exposure to Investigational Product

Descriptive statistics will be produced to describe the exposure to investigational product by treatment group. Compliance to each IP will also be summarized.

Page 59 of 67

Protocol Number: 20200058 Date: 07 February 2023

Treatment duration will be summarized by treatment group for the Placebo-controlled Phase using the safety population.

Summary statistics for treatment duration (in weeks), as well as a frequency summary of treatment duration categories (e.g., < 4,  $\ge 4$  - < 8 weeks, etc.) and exposure categories (e.g.,  $\ge 1$  day,  $\ge 4$ ,  $\ge 8$  weeks, etc.), will be provided.

Treatment duration (in weeks) is calculated as (the date of the last dose of IP – the date of the first dose of IP + 1) / 7 and rounded to one decimal place.

When partially missing last dose date is available, set last dose date to the maximum of [the earliest possible date given the non-missing field(s) of last dose date, the minimum of (the latest possible date given the non-missing field(s) of last dose date, last known date in database, first non-missing Early Termination (ET) visit date)].

When the last dose date is completely missing, set the last dose date to the minimum of (the last known date in database, first non-missing Early Termination (ET) visit date).

Last known date in database is defined as maximum of (last visit date, clinical efficacy assessment date, lab, vital signs, AE start or end dates, concomitant medications start or end dates, concomitant procedure date, treatment exposure start date or end date where doses were completely or partially taken, death date).

The specific definitions of the first and last dose dates for the Placebo-controlled Phase and Apremilast-exposure Period are given below:

- Placebo-controlled Phase:
  - First dose date: The date of the first dose of IP.
  - Last dose date:
    - the date prior to Week 16/Visit 5 for placebo-treated subjects who escape early at Week 16/Visit 5 and take at least one dose of IP dispensed at that visit, or
    - the date prior to Week 24/Visit 6 for subjects who complete Week 24/Visit
       6 dose, except for placebo-treated subjects who escape early
    - For all other subjects (i.e., subjects who discontinue prior to Week 24/Visit 6), the date of the last dose of IP in the study.

Page 60 of 67

Protocol Number: 20200058 Date: 07 February 2023

e: 07 February 2023 Page 61 of 67

- Apremilast-exposure Period:
  - First dose date:
    - The date of the first dose of apremilast after being randomized (at Week 0/Visit 2) or transitioned (at Week 16/Visit 5 or Week 24/Visit 6) to apremilast.
  - Last dose date:
    - The date of the last dose of apremilast.

The treatment compliance (in %) for each subject will be computed as 100 times the total number of tablets taken (the total number of tablets dispensed minus the total number of tablets returned) over the analysis phase or period divided by the intended total number of tablets that should have been taken over the same phase or period.

Summary statistics for compliance (%) will be provided by treatment arm for each analysis phase or period. Frequency summary tables of compliance will also be presented with the following categories: < 75%,  $\ge 75\%$  -  $\le 120\%$ , and > 120%.

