Week (Visit Window)	-28 Days	Week 0	4 (±3 days)	12 (± 3 days)	16 ^a (±3 days)	24 ^b (±3 days)	28° (±3 days)	40 (± 1 week)	48 (±1 week))	ET ^d	Obs. Follow-up Visit ^c 4 wks after the last dose of IP (± 7 days)
Patient's Assessment of Pain (VAS)	-	X	X	X	X	X	X	X	X	X	-
Dactylitis j	X										
Enthesitis assessment- LEI	-	X	X	X	X	X	X	X	X	X	-
HAQ-DI	-	X	X	X	X	X	X	X	X	X	-
BSA	-	X	X	X	X	X	X	X	X	X	-
PROs/QOLs											
PsAID-12					X						

Table 13: Table of Events (Continued)

	Screening		Placebo-controlled Phase				E	xtension Pha	Early Termination Visit	Observational Follow-up- Phase	
Visit Number	1 Screening	2 Baseline	3	4	5	6	7	8	9	Early Termination	10
Week (Visit Window)	-28 Days	Week 0	4 (±3 days)	12 (± 3 days)	16 ^a (±3 days)	24 ^b (±3 days)	28° (±3 days)	40 (± 1 week)	48 (±1 week))	ET ^d	Obs. Follow-up Visite 4 wks after the last dose of IP (± 7 days)
Health Economics Assessment											
Durtus											
Dosing Dispense Study Drug	1	X	Х	X	X	X	Х	X			
Return/Count Study Drug	-	-	X	X	X	X	X	X	X	X	-
BID = twice daily; BSA = Body Questionnaire – Disability Index Follow-up Visit = Observational	; IP = Investig	ational Pro		ported Outc	omes; PsAII	LEI = Leed	ls Enthesitis	Index;	otential; HAQ	D-DI = Health As	sessment Obs.

QOL = Quality of Life;

VAS = Visual

Analog Scale;

- ^a At the Week 16 Visit, subjects with no improvement in SJC (sentinel joints) at Week 16 are eligible for early escape, at the discretion of the Investigator and will receive treatment with apremilast 30 mg BID. The joints monitored for early escape must correspond to those affected at the Baseline Visit (sentinel joints).
- b All subjects who complete the Week 24 Visit will enter Extension Phase and receive apremilast 30 mg BID. The original treatment assignments (apremilast 30 mg BID or placebo) will remain blinded until the end of the study.
- ^c Beginning at the Week 28 Visit, all subjects in the Extension Phase will be dispensed open-label apremilast (30 mg BID) in high-density polyethylene (HDPE) bottles. Subjects must be clearly instructed to follow dosing instructions.
- ^d Subjects who discontinue the study prior to the Week 48 Visit, will have an Early Termination (ET).
- ^e The Observational Follow-up Visit will be conducted 4 weeks after the last dose of IP (± 7 days).
- f If an on site study visit is replaced with a telemedicine assessment, vital signs will not be measured.

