# 5.2 Derivations of Safety Endpoints

Baseline definition for all safety endpoints is given in Section 5.3. Change from baseline is calculated as on-treatment value minus the baseline value. Handling of time points is described in Section 5.4.

Treatment-emergent Adverse Event

An AE is a treatment-emergent AE (TEAE) if the AE start date is

- on or after the date of the first dose of investigational product (IP) and no later than 28 days after the last dose of IP for subjects who have completed the study or have discontinued early by the time of database cut, or
- on or after the date of the first dose of IP for subjects who are ongoing at the time of database cut

Protocol Number: 20200058

Date: 07 February 2023

Page 31 of 67

If the treatment-emergent status of an AE is unclear due to a missing/incomplete start date, it will always be considered treatment-emergent, unless shown otherwise by data. Date imputation rules for partially missing AE start dates are described in Section 8.3.1

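### With no usable last-dose date and no Early Termination Visit, SAP 9.6.9 can place the last dose in the off-drug follow-up

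*SAP*

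**What the plan says.** SAP 9.6.9 (Exposure to Investigational Product) gives the rules for an incomplete last-dose date.

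- **Completely missing date:** "set the last dose date to the minimum of (the last known date in database, first non-missing Early Termination (ET) visit date".
- **Partly missing:** the upper bound is "the minimum of (the latest possible date given the non-missing field(s) of last dose date, last known date in database" and the first ET visit date. The result may not fall before the earliest date that the recorded fields allow.
- **How the last known date is built:** "Last known date in database is defined as maximum of (last visit date, clinical efficacy assessment date, lab, vital signs, AE start or end dates". The list goes on through concomitant medications and procedures and ends with "treatment exposure start date or end date where doses were completely or partially taken, death date". Only the exposure term is tied to dosing.

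Two footnotes to the protocol's Table of Events (Table 13) decide who is capped. On the ET visit: "Subjects who discontinue the study prior to the Week 48 Visit, will have an Early Termination (ET". On the off-drug visit: "The Observational Follow-up Visit will be conducted 4 weeks after the last dose of IP (± 7 days".

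For the Placebo-controlled Phase, SAP 9.6.9 sets the last dose to the day before the Week 24 visit for Week 24 completers. For placebo subjects who escape early it is the day before the Week 16 visit. Neither uses the imputation. All other subjects, and everyone in the Apremilast-exposure Period, use the actual last-dose date.

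Treatment duration feeds the exposure-adjusted incidence rate (EAIR) of SAP 9.6.1: a subject without the event contributes the whole duration to the denominator. SAP 5.2 counts an adverse event as treatment-emergent if it starts "on or after the date of the first dose of investigational product (IP) and no later than 28 days after the last dose of IP". SAP 5.5 uses the same 28 days for the safety stop dates. Neither section says whether the last dose there means the imputed date.

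**The concern.** The rule takes the earlier of two dates, but the second exists only for a subject with an ET visit. Without one, the minimum has a single term and the rule returns the latest date on file. For a Week 48 completer that is at least the follow-up visit, planned for a time when the subject is off drug. A discontinuer can also lack an ET visit: protocol 11.1 lists death and loss to follow-up among the reasons for stopping, and 6.3.1 allows the follow-up contact by telephone.

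Two outputs are at stake. Exposure is overstated, which lowers the EAIR. And if the imputed date also defines the treatment-emergent window, an event well after the last dose could be tabulated as treatment-emergent. AE start dates and the death date are inside the maximum. So for a subject with neither a last-dose date nor an ET visit, no recorded event could fall outside a window built on that maximum.

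**Working it through.** The SAP gives no numerical result for this rule, so there is no figure to reproduce. The check applies the rule to subjects whose true last dose is taken as known.

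**Inputs.** Full treatment is 48 weeks = 336 days (protocol 3.3). Follow-up is 28 ± 7 days after the last dose, so 21 to 35 days (Table 13). Duration in weeks = (last dose − first dose + 1)/7 (SAP 9.6.9); with the first dose on day 1 this is L/7, where L is the day of last dose. The treatment-emergent window ends at L + 28 (SAP 5.2). With K the last known date and E the ET visit date, L = min(K, E) if an ET visit exists, and L = K if not.

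**1. Week 48 completer, last-dose date missing, true last dose day 336, no ET visit, follow-up visit the latest date on file.**

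| Follow-up after last dose | Imputed duration | True duration | Excess | Window would end, days after true last dose |
|---|---|---|---|---|
| 21 days | 357/7 = 51.0 weeks | 48.0 | 21/336 = 6.3% | 21 + 28 = 49 |
| 28 days | 364/7 = 52.0 weeks | 48.0 | 28/336 = 8.3% | 28 + 28 = 56 |
| 35 days | 371/7 = 53.0 weeks | 48.0 | 35/336 = 10.4% | 35 + 28 = 63 |

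The last column applies only if the imputed date is used in SAP 5.2.

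**2. Discontinuer with an ET visit, true last dose day 60.** Only the gap to the ET visit counts: 0 days gives 8.6 weeks (no excess), 7 days gives 67/7 = 9.6 weeks (+11.7%), 14 days gives 74/7 = 10.6 weeks (+23.3%). Follow-up, later medication or AE dates and death cannot enter.

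**3. Discontinuer without an ET visit, follow-up contact at 28 days.**

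| True last dose | True weeks | Imputed weeks | Excess |
|---|---|---|---|
| Day 30 | 4.3 | 58/7 = 8.3 | 28/30 = 93% |
| Day 60 | 8.6 | 88/7 = 12.6 | 28/60 = 47% |
| Day 112 | 16.0 | 140/7 = 20.0 | 28/112 = 25% |

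If instead the latest date is a death or late-reported SAE 60, 90 or 180 days after a last dose on day 112, the imputed durations are 172/7 = 24.6, 202/7 = 28.9 and 292/7 = 41.7 weeks, against 16.0.

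**4. Partly missing date, no ET visit.** With only the year recorded, the upper bound is the earlier of 31 December and K. If follow-up falls in the same year, the result is as in step 1. With month and year recorded, the imputed date stays in that month.

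**5. Effect on total exposure.** The number of missing dates is not given. If a share m of subjects gains 28 days on a 336-day base, exposure rises by m × 28/336. For m = 1% that is 0.08%, for 5% it is 0.42%, for 10% it is 0.83%. On a 168-day (24-week) base these double.

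**6. The same completer with a Week 48 cap.** At the target day of 337 (SAP Appendix A), 337/7 = 48.1 weeks, against a true 48.0.

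**The case against.** A reader might infer that any missing last-dose date pushes the last dose to follow-up or death, so that exposure is generally overstated and off-treatment events become treatment-emergent. The documents do not support that, and most of the case against it stands.

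- **The ET cap.** Protocol Table 13 plans an ET visit for everyone who stops before Week 48, and protocol 6.2.1 asks for the end-of-treatment evaluation as soon as possible. With that visit on file, a death months later cannot become the last dose.
- **The randomised comparison.** Week 24 completers and early-escape placebo subjects have visit-based dates. Only subjects who discontinue before Week 24 without an ET visit can be affected there. The completer case concerns the Apremilast-exposure Period, which has no concurrent placebo group.
- **Event classification.** Events up to 28 days off drug are treatment-emergent by design, and routine AE recording stops at 28 days (protocol 6.5.8). A longer window would mainly add SAEs and deaths that become known later, which protocol 10.1 does collect. Its use of the imputed date is an inference, although the SAP offers no other rule for a missing last dose.
- **Compliance.** SAP 9.6.9 defines that denominator by the tablets intended over the phase or period, with no reference to the imputed date.
- **Frequency.** The follow-up visit is timed from the last dose and drug is counted at each return visit, so a completer with no last-dose date should be uncommon.

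It can also be said that counting doubtful events as treatment-emergent matches the SAP's cautious handling of unclear AE start dates. That is fair for event counts. It does not carry over to the denominator, where longer exposure lowers the rate.

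What remains is the uncapped group. There the rule as written returns a date on which, by the trial's own schedule, the subject is off drug.

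**Conclusion.** A minor point, but the rule is wrong as written. It applies where the last-dose date is completely missing or only its year is recorded, and there is no ET visit. An affected Week 48 completer is credited with about 52 weeks (51 to 53) instead of 48, and the EAIR denominator in the Apremilast-exposure Period rises with it. This assumes that the true last dose was at 48 weeks and that the follow-up visit is the latest date on file. A discontinuer without an ET visit can have a larger individual error.

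If 1% to 5% of subjects are affected, by 4 weeks each on 48, total exposure changes by about 0.1% to 0.4%. That share is an assumption. The primary and secondary efficacy tests do not use this date.

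The effect on event tables is conditional. Only if the imputed date is meant in SAP 5.2 and 5.5 does the window run to about 56 days (49 to 63) after a completer's true last dose. Even then it matters chiefly for a late-reported SAE or death. The SAP should settle which reading applies.

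**What to change.** In SAP 9.6.9:

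1. For subjects who complete Week 48, add the Week 48 visit date to the minimum. Table 13 shows no drug dispensed at that visit.
2. Exclude the Observational Follow-up Visit, and dates recorded only at or after it, from the last known date.
3. State in 5.2 and 5.5 whether the last dose means the imputed date.

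Two tempting alternatives should be avoided: capping at the last visit where drug was returned or counted, and dropping the death date for subjects who may still have been dosing. Weeks 28 and 40 are 12 weeks apart. Take a subject who returns and receives drug on day 197 (the Week 28 target), has no ET visit or recorded last dose, and dies while dosing on day 260. Those changes would set the last dose to day 197 and, if that date drives the window, end it on day 197 + 28 = 225. An on-treatment death would then drop out of the treatment-emergent tables. The present rule keeps it.

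The cost is a few sentences of SAP text and a small change to the exposure program, with no new data collection.
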